### **Functional magnetic resonance imaging (fMRI)**

We are collecting pre-implantation fMRI in order to localize the neural representations of movements of the upper limb, wrist, hand, and/or fingers. This information will be combined with anatomical information, clinical judgment, and intraoperative stimulation and recording to select the cortical implant placement site. After explantation surgery, we will be collecting fMRI to determine if training and use of the Neural Bridging System has resulted in any change in the locations of neural representations of movements of the upper limb, wrist, hand, and/or fingers. In both pre-implantation and post-explantation fMRI sessions, we will ask the participant to complete a task with visual and/or auditory stimuli designed to evoke neural representations of the movements of interest.

### **Transcranial magnetic stimulation (TMS)**

To complement the fMRI motor mapping of the motor cortex that is being used for pre-surgical implant location planning and post-explant evaluation of motor cortex plasticity, we will also include transcranial magnetic stimulation (TMS) pre-implant and post-explant to map the hand and arm area of the motor cortex. TMS is a non-invasive brain stimulation method that delivers a magnetic pulse through the surface of the skull to the motor cortex. This induces a depolarization of neurons in the corticospinal tract, which results in a twitch of peripheral limb muscles innervated by that brain region. This modality is commonly used clinically as an alternative to fMRI for pre-surgical motor mapping to assist in planning prior to brain surgery. It is used experimentally to investigate corticospinal tract plasticity associated with motor recovery, e.g., after stroke. Potential risks include seizures (2%, mostly among patients who were previously known to have seizures) and headache. Mapping of the hand/arm area with MRI-navigated TMS in patients with spinal cord injury serves 3 purposes: 1) it validates the cortical motor maps obtained through fMRI; 2) it distinguishes the sectors of cortical motor maps that are capable of controlling voluntary motion through the corticospinal tract in the spinal cord from areas that have been rendered mute from cord injury; and 3) it allows for quantification of plasticity, or change in sectors of motor maps that are capable of controlling voluntary motion through the corticospinal tract after stimulator explant.

We will perform TMS pre-implant (baseline, phase I) and post-explant (follow-up, phase IV).

We will deliver navigated TMS based on the patient's brain MRI scans to stereotactically identify and target near the "hand knob" of the primary motor cortex on the central sulcus.

Recording EMG electrodes will be placed on the skin surface above the most distal upper limb motor groups under voluntary control by the patient, as defined by the pre-implant EMG study, as well as the extensor digitorum communis (EDC) and the abductor pollicis brevis (APB). We will find motor threshold, defined as the lowest stimulation intensity that produces a motor evoked potential, or EMG twitch response, of 100-500uV in the target voluntary muscle group on at least 50% of trials. We will start at an intensity of about 35% of stimulator output, adjust intensity up if needed until we are able to see twitch responses, then use a staircase method to adjust intensity up/down to find the motor threshold. The staircase will lower stimulation intensity 1-2% for trials with an EMG peak-to-peak response >500 uV or increase the intensity 1-2% for trials with EMG responses <100 uV.

Using the 110% of the MT intensity defined in the previous step, we will determine the spatial extent of the upper limb cortical motor map by stimulating over a grid overlaying the central sulcus, precentral gyrus, postcentral sulcus and precentral sulcus and reporting locations with motor evoked potentials (MEPs).

### **3.3 Outcomes and Data Analysis**

Statistical analysis will be conducted with a biostatistician consultant. Continuous outcome variables will be summarized by the mean, median, standard deviation, minimum and maximum. Adverse effect data will be reported continuously, including all serious and non-serious adverse effects, as well as effects related to the surgical procedure and device-related.

### **Primary and Secondary Outcomes**

The primary outcome measure of this study is the achievement of voluntary movement of the upper extremity. Based on previous neural decoding that has been demonstrated in humans (Bouton 2009), it is expected that many of the following movements will be recognizable and classifiable in the motor cortex and can be achieved physically through the multichannel

stimulator: wrist flexion, extension, adduction, and abduction; forearm pronation/supination; flexion and extension of fingers.

The targeted primary and secondary outcomes are therefore as follows:

- Primary outcome- consistent and repetitive voluntary movement in the targeted muscle groups
- Secondary outcome- consistent movement in the targeted muscle groups that is functional (manipulate or pick up an object)

## **4. Risk Analysis**

### **4.1 Risks**

The surgical risks for implantation are the same as for any intracranial craniotomy, image guided procedures and implantable device such as a deep brain stimulator or a motor cortex stimulator procedure. This includes hemorrhages (intraparenchymal, subdural or epidural hematoma), paralysis, coma and/ or death, stroke, leaking of fluid surrounding the brain, seizures, infection, allergic reaction, temporary or permanent neurological complications, confusion or attention problems, pain at the surgery sites and headaches.

Training and therapeutic sessions involving BCI regulated functional electrical stimulation will need to be monitored for autonomic dysreflexia signs and symptoms.

As with any muscle stimulator, there can be a risk of excessive current and skin irritation or burns. The stimulator in the Neural Bridging System, however, limits the average output current density to less than  $2\text{mA/cm}^2$  at the skin and the average power density to less than  $0.25\text{W/cm}^2$  to provide safe levels and avoid tissue damage. Despite these built-in safety limits, current and power density could exceed FDA guidelines if electrodes lift off the skin. This has the potential to cause causing minor irritation or first degree burns locally. The research investigator will monitor frequently during test sessions for wrinkles and misalignment of the sleeve, and any signs of electric shock, skin irritation, and/or burns.

The sleeve material itself is spandex, with registration marks printed on it. The material itself has been formally tested for biocompatibility, both in vitro and in vivo, prior to printing and laundering. The printed, laundered sleeve was tested in Battelle's IRB-approved Able-bodied study for up to 8 hours, with and without similar nontoxic conductive lotion. No adverse skin

reactions were observed. The investigator, who will already be monitoring frequently for signs of irritation from electric shock, will also monitor for signs of allergic skin reaction.

When using virtual reality (VR) systems, there is the risk of feeling nauseous, disoriented or dizzy, similar to sensations of motion sickness. About 1 in 4,000 people using VR systems have a risk of seizures, similar to the risk of having a seizure while watching TV. Showing incongruent movements on the virtual reality headset may cause confusion or frustration. The researchers will monitor participants closely for signs or symptoms of confusion that may occur.

The study Sponsor-investigator and co-investigators will be responsible for the evaluation, monitoring, and documentation of events meeting the criteria and definition of an adverse event (AE) or serious adverse event (SAE) as provided in this clinical investigation. The study participants will be evaluated for any possible AEs from the time written study informed consent is obtained until study closure or the subject exits the study.

- Any normal expected postoperative complaints or symptoms, unless the event involves a clinically significant change in a patient's severity or duration of symptoms, or that requires clinical intervention other than the ordinary postoperative care. The following are some expected postoperative outcomes that *may* occur: headache, autonomic dysreflexia, incision pain, nausea, vomiting, low grade fever, dizziness, sleepiness, nervousness, insomnia, constipation, urinary retention, confusion, etc.
- Any pre-existing condition unless a worsening of that condition in terms of nature, severity, or frequency develops.
- Medical or surgical procedure unrelated to the clinical protocol (i.e., dental or cosmetic procedure)
- Technical observation or a device events that does not result in a medically undesirable situation for the subject

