#### **4.1.1 Safety Endpoints**

The study safety endpoints will include a characterization of all adverse events (AE) for all participants, including those related to the implant surgical procedure, the implantable device,

and stimulation of patients with tetraplegia. In addition, these safety profile elements will be compared across the various phases of the study. Furthermore, patients with clinically significant complications related to surgery (hemorrhage, stroke, infection) will not undergo implantation or further participation in the study.

Participants may choose to withdraw from the study at any point, in addition, the study investigators may decide to conclude a patient's participation in the study for the following medical reasons:

- Onset of epilepsy;
- Significant decrement in neurological exam;
- Development of serious adverse events, physical or psychological, including negative behavioral symptoms, major depression, or suicidal ideation;
- Intra- or extra-cranial infection unresponsive to antibiotic treatment;
- Serious infection around the percutaneous connector unresponsive to antibiotic treatment;
- Development of intracranial hematoma requiring evacuation; and
- Need for urgent Magnetic Resonance Imaging (MRI) of any kind (brain or body).

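### Section 4.1 appears to exempt ordinary postoperative symptoms from adverse-event counting, including named surgical risks, so the safety endpoint will miss mild surgical events and may miss some autonomic dysreflexia

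*Combined protocol and SAP*

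**What the plan says.** Section 4.1.1 sets the safety endpoint broadly: "The study safety endpoints will include a characterization of all adverse events (AE) for all participants". It includes events related to the implant surgery, the device and stimulation, and says the safety profile will be compared across study phases. Section 3.3 likewise promises reporting of all serious and non-serious effects, surgical ones among them. Section 4.1.4 requires all AEs from consent to explantation to be logged.

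Section 4.1 closes with four bullets. The first covers "Any normal expected postoperative complaints or symptoms, unless the event involves a clinically significant change in a patient's severity or duration of symptoms", with a second exception for an event "or that requires clinical intervention other than the ordinary postoperative care". Its examples are "headache, autonomic dysreflexia, incision pain, nausea, vomiting, low grade fever, dizziness, sleepiness, nervousness, insomnia, constipation, urinary retention, confusion, etc". The second bullet covers "Any pre-existing condition unless a worsening of that condition in terms of nature, severity, or frequency develops".

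Earlier in the same section, the surgical risks include "confusion or attention problems, pain at the surgery sites and headaches". Stimulation sessions "will need to be monitored for autonomic dysreflexia signs and symptoms". For the virtual-reality (VR) headset, "there is the risk of feeling nauseous, disoriented or dizzy, similar to sensations of motion sickness", and incongruent displays are said to carry a risk of confusion.

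**The concern.** A safety endpoint that covers all AEs is only as complete as the rule that decides what an AE is. If that rule drops symptoms which the protocol itself lists as risks of the operation, a low count of them says little about the operation.

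The rule also acts before attribution. Section 4.1.4 has relatedness judged for all events, but an exempt symptom never becomes a logged event, so nobody rates it. Someone must first decide that it is normal, expected and handled by ordinary care, and the protocol defines none of these terms.

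The comparison across phases is at stake too, because the first bullet works only after surgery. The same mild headache can be counted in one phase and left out in another.

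**Working it through.** No sample-size, power or event-rate figure bears on this point, so the check is a comparison of text plus a count.

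**1. What the bullets do.** The text as available has no lead-in to them. Each is built on an exception or a negative: unless worse, unrelated to the protocol, no undesirable result for the participant. They make sense only as a list of what is not counted as an AE. This is an inference. A lead-in may have been lost when the file was converted, so its absence is not held against the plan.

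**2. Overlap with named risks.** The first bullet gives 13 examples and then stays open-ended.

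| Source of risk in 4.1 | Also among the 13 examples |
|---|---|
| Surgery | headache, site pain, confusion |
| Stimulation sessions (to be monitored for) | AD |
| VR headset | nausea, dizziness, confusion |

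Confusion appears twice, so the distinct overlap is 3 + 1 + 2 = 6 of 13. Only the 3 surgical ones are squarely postoperative. For the other 3 (AD, nausea, dizziness), section 4.1 ties the risk only to stimulation or VR.

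**3. Effect on surgical events.** A headache after craniotomy that follows the usual course and needs only ordinary care meets neither exception, so it is not an AE under 4.1. Yet it is a named surgical risk, and sections 3.3 and 4.1.1 say that effects of surgery are covered. The two rules conflict for this class of event.

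**4. Effect on the phase comparison.** The protocol gives no rates, so take an assumption: k of 5 participants have one ordinary postoperative headache and nothing more. Under the first bullet the surgical-phase log shows 0/5 = 0% for every k from 0 to 5, while the true proportion, k/5, runs from 0% to 100%. A new headache of the same grade in Phase I or Phase III is not postoperative and would be logged. The contrast between phases is thus partly set by the definition.

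**5. The missing window.** Section 3.2 gives the surgery phase about 1–2 weeks, and the surgical recovery text in 3.2.2 gives 1–2 weeks, possibly longer. The first bullet refers to neither, so the end of the postoperative period is left to the person coding the event.

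**6. AD during stimulation.** The only AD criterion in 3.1.1 concerns poorly controlled AD, so people with controlled AD can enrol. The pre-existing-condition bullet carries no postoperative limit and so applies in Phase III. An episode provoked by stimulation, of usual character, could be classed as pre-existing and not worsened. A rise in frequency would count as worsening, but it can be seen only if each episode is recorded, and section 4.1 asks for monitoring without saying that episodes are to be recorded.

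**The case against.** The strongest reply is that the first bullet is narrow. It covers only normal expected postoperative complaints and has two exceptions, so a prolonged headache, or confusion needing more than ordinary care, remains an AE. Exempting routine postoperative complaints is a recognised convention, and this is a proof-of-concept study of at most 5 participants that will not support an approval submission (4.5). All of that stands, and it limits the certain loss to mild surgical events. It does not remove the conflict with an endpoint described as covering all AEs, nor the effect on the phase comparison.

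A reader might go further and infer that all six overlapping symptoms drop out for the whole study. The documents do not support this. Nausea or dizziness from a headset, or AD in a session long after surgery, is not a postoperative complaint on a plain reading and stays reportable. For those events the open list and the missing window leave room for inconsistent coding, no more.

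A reader might also infer that AD in someone with a history of it can never be counted. That is too strong as well: worsening in nature, severity or frequency still counts, and episodes added by stimulation may well be a worsening in frequency. Nor can it be said that AD has no other place to be recorded, since the case report forms and the full hazard analysis are not in the text available. Reporting to the data and safety monitoring committee is no argument either way, because section 4.1.5 commits only serious events to it.

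**Conclusion.** The point holds in limited form. Mild surgery-related headache, site pain and confusion, 3 of the 13 listed examples, will be left out of the safety endpoint although section 4.1 names them as surgical risks. The surgical phase will look safer partly by definition. For stimulation and VR sessions, under-counting is a possibility only, and the pre-existing-condition bullet applied to controlled AD is the most concrete route.

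The number of events lost cannot be estimated without rates. The conclusion assumes that the four bullets list events not counted as AEs, which their wording strongly suggests but which no visible sentence states. The plan should be changed, but this does not undermine the study as a whole.

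**What to change.** Reconcile sections 3.3, 4.1, 4.1.1 and 4.1.4 so that one recording rule applies:

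- Enter every listed symptom in the AE log with onset date, study phase and relatedness. The relatedness scale in 4.1.4 is worded around stimulation, so add an entry for relation to surgery.
- Replace the exemption with an *expected postoperative* flag, allowed only when onset falls within a stated window after implant or explant surgery. General logging under 4.1.4 stops at explantation, so it must run to the end of the second window.
- Delete *etc.* from the list.
- Log any AD episode during or after a stimulation session, whether or not AD is pre-existing.
- Report flagged and unflagged events separately, by phase.

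This keeps the distinction between expected and unexpected symptoms but moves it from recording to analysis. It changes what is written down, not how participants are managed. The cost is protocol wording, some extra lines in an existing log for at most 5 participants, and AE counts that look less favourable.

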#### **4.1.1 Safety Endpoints**

The study safety endpoints will include a characterization of all adverse events (AE) for all participants, including those related to the implant surgical procedure, the implantable device,

and stimulation of patients with tetraplegia. In addition, these safety profile elements will be compared across the various phases of the study. Furthermore, patients with clinically significant complications related to surgery (hemorrhage, stroke, infection) will not undergo implantation or further participation in the study.

Participants may choose to withdraw from the study at any point, in addition, the study investigators may decide to conclude a patient's participation in the study for the following medical reasons:

- Onset of epilepsy;
- Significant decrement in neurological exam;
- Development of serious adverse events, physical or psychological, including negative behavioral symptoms, major depression, or suicidal ideation;
- Intra- or extra-cranial infection unresponsive to antibiotic treatment;
- Serious infection around the percutaneous connector unresponsive to antibiotic treatment;
- Development of intracranial hematoma requiring evacuation; and
- Need for urgent Magnetic Resonance Imaging (MRI) of any kind (brain or body).

#### **4.1.2 Serious Adverse Events**

A Serious Adverse Event (SAE) is an adverse event that is fatal or life-threatening, permanently disabling, requires or prolongs hospitalization, or results in significant disability, congenital anomaly, or birth defect (OSU IRB Policy v 12/19/16).

#### **4.1.3 Unanticipated Adverse Device Effects**

An unanticipated adverse device effect (UADE) is defined as any serious adverse effect on health or safety or any life-threatening problem or death caused by, or associated with the device [and/or stimulation therapy] if that effect, problem, or death that was not previously identified in nature, severity, or degree of incidence in the investigational plan or application (including a supplementary plan or application), or any other unanticipated serious problem associated with a device that relates to the rights, safety, or welfare of participants (21 CFR 812.3(s)).

Any UADE will result in an evaluation of that effect as soon as is possible, and will then be reported to the IRB within 10 days (OSU IRB policy v 12/19/16) and to the FDA within 10

working days after the sponsor-investigator first receives notice of the effect(s). [21 CFR 812.46(b), 812.150(a)(1), 812.150(b)(1)]

### **Device Malfunction**

A device malfunction is the failure of a device to meet its performance specifications or other performance as intended. Performance specifications include all claims made in the labeling for the device. The intended performance of a device refers to the intended use for which the device is labeled or marketed (21 CFR 803.3(k)).

#### **4.1.4 Documentation of Adverse Events**

All AEs from the time the study informed consent is signed through the time of device explantation will be recorded as AEs on the study adverse event log; each event being documented separately. Any adverse event occurring after this time and is considered related to the device or therapy by the Principal Investigator will be reported. AEs and SAEs will be followed until:

- AE is resolved and has returned to normal/baseline or has stabilized
- Subject has withdrawn from the study
- AE is judged by the investigator to be no longer clinically significant
- Study closure at which time, the responsibility for following any ongoing AEs will be transferred to the incoming clinical care team.

The Principal Investigator will serve as point of contact to which the team will report adverse events. All non-serious adverse events will be reported to the FDA and to The Ohio State University Institutional Review Board (IRB) during the annual reporting period.

Relatedness will be determined for all events according to the following criteria:

- **Definitely related:** The event is resolved by discontinuing stimulation and another cause cannot be identified.
- **Probably related:** The event resolves upon discontinuing stimulation and cannot be reasonably explained by the subject's current clinical state or any other cause.

- **Possibly related:** The event was likely caused by the subject's current clinical state, , however, the effect of stimulation cannot be ruled out.
- **Unlikely related:** The event did not occur temporally to stimulation and can be explained by the subject's current clinical state or any other cause.
- **Unrelated:** The event is explained by the subject's current clinical state or any other cause.

For purposes of determination of a UADE the following categories will be considered related: “definitely related” and “probably related”.

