#### **4.1.5 Reporting of Serious Adverse Events**

SAEs reported during the protocol defined reporting period per section 4.1.4 will be:

- Evaluated for their relatedness per section 4.1.4;
- Reported to the Data Safety Monitoring Committee;
- Included in the IRB Continuing Review; and
- Included in the FDA Annual Report.

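### The relatedness scale that decides UADEs depends on stopping stimulation, so array harms and deaths cannot qualify; and full AE logging ends at explantation, before safety follow-up does

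*Combined protocol and SAP*

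**What the plan says.** **Relatedness.** Section 4.1.4 introduces a single scale: "Relatedness will be determined for all events according to the following criteria". The top tier reads "The event is resolved by discontinuing stimulation and another cause cannot be identified". The next begins "The event resolves upon discontinuing stimulation and cannot be reasonably explained". The section then restricts the UADE decision: "For purposes of determination of a UADE the following categories will be considered related", and it names only those two tiers. Section 4.1.3 defines a UADE more widely, as a serious unanticipated effect, problem or death linked to the device, to stimulation therapy, or to both. Section 4.1.1 lists the implant operation, the implantable device and stimulation as separate sources of AEs.

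**Logging window.** Section 4.1.4 states: "All AEs from the time the study informed consent is signed through the time of device explantation will be recorded as AEs". For the time after that: "Any adverse event occurring after this time and is considered related to the device or therapy by the Principal Investigator will be reported". Section 4.1.5 takes its period from the same place: "SAEs reported during the protocol defined reporting period per section 4.1.4 will be" assessed for relatedness, sent to the safety committee, and included in the IRB continuing review and the FDA annual report.

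Other sections are wider. Section 4.1 makes the investigators "responsible for the evaluation, monitoring, and documentation of events meeting the criteria and definition of an adverse event" and has participants evaluated for AEs until the study closes or they leave it. Section 3.3 reports all adverse effects, serious or not, including surgical and device effects, and gives no cut-off. Section 4.1.1 characterizes all AEs in all participants and compares them across phases.

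**The concern.** The scale is the gate to UADE classification, and 4.1.3 attaches reporting deadlines to UADEs: 10 days to the IRB and 10 working days to the FDA. If the gate recognizes only events that go away when stimulation stops, it leaves out harm from the study's most invasive component, the array in the cortex. That array records; stimulation is delivered separately at the skin.

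The logging cut-off is a matter of ascertainment. The weeks after explantation follow a second intracranial operation, whose risks section 4.2 likens to those of insertion. They include the repeat TMS session. They also include the repeat neuropsychological tests, which section 3.2.5 uses to judge whether function declines after explant. If capture in that period depends on one person's causal judgement, a comparison of AEs across phases is not like with like, and the expected direction is too few harms counted after explantation.

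**Working it through.** The plan gives no figure to reproduce. The check is a comparison of texts plus a count of exposure.

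**Step 1: what each tier of 4.1.4 refers to.**
- Definite: resolved by stopping stimulation, no other cause. Refers to stimulation; counts for a UADE.
- Probable: resolves on stopping stimulation, not otherwise explained. Refers to stimulation; counts for a UADE.
- Possible: clinical state the likely cause, stimulation not excluded. Refers to stimulation; does not count.
- Unlikely: not close in time to stimulation, otherwise explicable. Refers to stimulation; does not count.
- Unrelated: explained by clinical state or another cause. Names no study exposure; does not count.

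Tiers referring to stimulation: 4 of 5. Tiers naming surgery, the array or another study procedure: 0 of 5. UADE tiers that require resolution on stopping stimulation: 2 of 2.

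**Step 2: put cases through the scale.**
- A death cannot resolve, so it meets neither UADE tier, whatever caused it. Section 4.1.3 names death explicitly.
- A serious unanticipated harm from the array has no reason to end when surface stimulation is switched off. It fails the definite tier, and could meet the probable tier only through coincidence of timing. Read literally, the array is another cause, which points to unlikely or unrelated.
- A harm first arising after explantation has no ongoing stimulation to discontinue.

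So 4.1.4 is narrower than the definition in 4.1.3 that it is meant to apply.

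**Step 3: how long the scale problem applies.** Approximate phase lengths from section 3.2, at 4.35 weeks per month: 8 weeks baseline + 1 to 2 weeks surgery + 60 × 4.35 = 261 weeks decoding and stimulation + 8 weeks follow-up = 278 to 279 weeks. From the surgery phase on, that is 278 − 8 = 270 weeks, or 270/278 = 97% of planned time per participant.

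**Step 4: size of the logging gap.** Section 3.1 plans up to 5 participants, and Phase IV lasts about 8 weeks: 5 × 8 = 40 participant-weeks at most. As a share of planned time, 8/278 = 2.9%. These figures describe only the logging gap, not the scale problem. The explant operation itself may fall inside the log, since logging runs through the time of explantation; the gap is the period after it.

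**Step 5: does other text close the gap?** Section 4.2 continues safety monitoring until all participants have finished, and section 5.1 has a committee evaluate accumulating data. Neither restores full logging.

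**The case against.** Several counter-arguments carry weight.

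*Evaluating is not recording.* A reader might infer that 4.1 and 4.1.4 flatly contradict each other. They need not: the time window in 4.1 governs evaluation, and its sentence on documentation has no window. One can read a tiered design: evaluate to exit, log everything to explantation, then report what is related. The period cited in 4.1.5 may likewise include that later tail. This reading is coherent, but it does not deliver the all-AE comparison across phases in 4.1.1.

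*Other reporting sentences have no cut-off.* Section 3.3 covers all serious and non-serious adverse effects, and 4.1.4 sends all non-serious AEs to the FDA and IRB annually. It therefore goes too far to say that events not rated related can never be reported. But neither sentence extends the log, so they add to the inconsistency.

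*Surgical complications and TMS seizures as lost UADEs.* A reader might infer this too. The documents do not support it. Infection, bleeding, further surgery and seizures are listed for removal (4.2), neurological complications for implantation (4.1), and seizure and headache for TMS (3.2.5). Events already identified in nature, severity and incidence are not UADEs under any scale, and TMS is not a component of the device described in 4.5. The problem is confined to unanticipated device harm, including known harms of greater severity or incidence than identified.

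*Limited stakes.* This is a feasibility study with descriptive summaries. Post-explant events considered related are still reported, and test scores exist apart from the AE log. Section 4.1 also appears to set aside ordinary postoperative complaints, so full logging may add few events. The case report forms were not available and may already record relatedness to procedure or device. These points bear on severity; they do not repair the wording.

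**Conclusion.** The point holds in two parts. The main one is that 4.1.4 ties the UADE decision to resolution on stopping stimulation, so a death or a serious unanticipated array harm cannot be classed as a UADE, contrary to 4.1.3. This runs from implantation on and rests on the wording alone.

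The second is that full logging ends at explantation while 3.3, 4.1 and 4.1.1 are wider. The phase comparison then sets full capture against capture selected by the Principal Investigator for about 8 weeks per participant, at most about 40 participant-weeks. This assumes full enrolment and the approximate phase lengths in 3.2. The direction is an under-count of harms after explantation. It is partial, and its size cannot be estimated: the documents give neither a post-explant complication rate nor the share of events that would be considered related.

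The primary outcome is unaffected. A reader might infer that the safety data are invalid or that post-explant harms are lost outright; neither follows, because related events are still reported and safety monitoring continues. Severity: should-fix.

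**What to change.** 1. In 4.1.4, rate relatedness separately to (i) implant and explant surgery, (ii) the implanted array, (iii) stimulation and (iv) other study procedures such as TMS. Use causal wording that depends neither on stopping stimulation nor on the event resolving. Base the UADE determination on the device and stimulation ratings, counting device effects that arise at implantation or removal, so that 4.1.4 matches 4.1.3. Ratings for TMS and other non-device procedures should not feed the UADE rule.
2. Reconcile 3.3, 4.1, 4.1.1, 4.1.4 and 4.1.5 so that all AEs and SAEs are logged and reported from consent to study exit, meaning the end of Phase IV.

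Cost: changes to protocol and case report form wording, and about 8 more weeks of logging per participant (at most about 40 participant-weeks) in a phase that already has post-surgical appointments and repeat testing. A few more events will be reported. Clinical management does not change.
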